The potential risk of disclosure of confidential information is guarded against by maintaining completed questionnaires, including ancillary questionnaires and blood test results in locked files accessible by authorized personnel only. In these files, participants are identified only by study ID. Subject identifiers are stored in separate computer files with password protection, and results will be presented only in the aggregate. In addition, employees involved with the proposed study will be asked to sign a form agreeing not to disclose any information to which they might have access, regardless of their personal perception about its confidentiality. Each employee of the study with human subject contact participates in an institutional (Brigham and Women's Hospital) human subjects educational program, which consists of reviewing regulatory and informational documents pertaining to human subjects research; passing a test on ethical principles and regulations governing human subjects research; and signing a statement of commitment to the protection of human subjects. Finally, all such employees are required to participate in HIPAA training. Medical records will be reviewed by Brigham and Women's physicians who have completed Human Subjects Certification.

SENDING SPECIMENS/DATA TO RESEARCH COLLABORATORS OUTSIDE PARTNERS

Specimens or data collected by Partners investigators will be sent to research collaborators outside Partners, indicate to whom specimens/data will be sent, what information will be sent, and whether the specimens/data will contain identifiers that could be used by the outside collaborators to link the specimens/data to individual subjects.

Specimens and data from this study will not be shared with collaborators outside of Partners.

Specifically address whether specimens/data will be stored at collaborating sites outside Partners for future use not described in the protocol. Include whether subjects can withdraw their specimens/data, and how they would do so. When appropriate, submit documentation of IRB approval from the recipient institution.

Not applicable.

RECEIVING SPECIMENS/DATA FROM RESEARCH COLLABORATORS OUTSIDE PARTNERS

When specimens or data collected by research collaborators outside Partners will be sent to Partners investigators, indicate from where the specimens/data will be obtained and whether the specimens/data will contain identifiers that could be used by Partners investigators to link the specimens/data to individual subjects. When appropriate, submit documentation of IRB approval and a copy of the IRB-approved consent form from the institution where the specimens/data were collected.

Not applicable.

Protocol Biostatistical Analyses

Separate analyses will be conducted for the 3 endpoints and for the 2 nutritional supplements, vitamin D and omega-3 fatty acids. Analyses of treatment effects will be based on the intent-to-treat principle. The first analysis will compare baseline characteristics by randomized treatment

assignment to ensure that balance was achieved by the randomization. Characteristics to be examined include known risk factors for autoimmune diseases, systemic inflammation, and chronic knee pain including: age; gender; race/ethnicity; family history of autoimmune disease; BMI; smoking; alcohol use; physical activity; co-morbid medical conditions such as hypertension, hyperlipidemia, diabetes, and cardiovascular disease; and baseline vitamin D and omega-3 fatty acid levels as assessed by dietary questionnaire in all participants and blood assays in the case-cohort subsample. The large sample size, as well as successful balance of known potential confounders, will provide assurance that unmeasured or unknown potential confounders will also be equally distributed across randomized treatment groups. For autoimmune disease, we will estimate the intervention effects on the primary endpoint of total incident autoimmune disease. For inflammatory biomarkers, we will assess changes in linear biomarkers (log transformed if necessary). For chronic knee pain, the primary endpoint will be assessed by the WOMAC pain scale; secondary analyses will test for decreases in WOMAC stiffness, function and global scales, as well as analgesic use separately. Data analyses will be performed using SAS 9.2 (SAS Institute Inc., Cary, North Carolina).

Autoimmune Disease Incidence. In this 2x2 factorial design, the primary aim is to compare the main effects of intention-to-treat with vitamin D and with fish oil upon autoimmune disease incidence. Initially, we will compare Kaplan-Meier curves to graphically display the survival functions across different treatment groups and a log-rank test to test the difference. We will use Cox proportional hazards models to assess the main and interaction effects of the treatment groups. The unadjusted risk ratios and their 95% CIs will be used to measure the strength of risk across different treatment groups. The proportional hazard assumption will be tested based on the smoothed plots of the scaled Schoenfeld residuals³⁸⁶. To estimate the cumulative incidence function, a nonparametric estimate will be obtained using the Kaplan–Meier method. Given randomization and blinding of 20,000 individuals in this RCT, most important covariates will be equally distributed. But, in secondary analyses, we will assess the effects of controlling for age, sex and other possible strong predictors, such as family history of autoimmune disease; baseline levels of inflammatory biomarkers, vitamin D, EPA and DHA; dietary vitamin D, EPA and DHA intake; BMI and physical activity.

Inflammatory Biomarkers. In a randomly selected subcohort of 2000 participants, blood will be collected at both baseline and follow-up and changes in levels of plasma biomarkers of inflammation will be investigated. As inflammatory biomarkers are associated with age, BMI, medication use and cigarette smoking, we will again ensure that baseline characteristics are balanced in the four treatment groups in this subcohort and will additionally adjust for them in our analyses. Inflammatory Biomarkers (hsCRP, IL-6, TNFR2) will be analyzed as continuous outcomes. Descriptive statistics such as the minimum, maximum, range, median, and mean are used to summarize the variable as well as detect outliers and missing values. Exploratory graphical techniques such as Boxplots, Histograms, Quantile-Quantile plots, and Stem and Leaf plots will be used to further examine the distribution of each biomarker. Natural log transformation may be necessary based on our past analyses¹⁰⁵. Unadjusted treatment effects will be evaluated using two-way Analysis of Variance (ANOVA) or Kruskal–Wallis nonparametric test. Multiple linear regression will be used to test the association between the biomarkers (or transformed scale) and treatment groups, while adjusting for age and gender. Model assumptions and goodness of fit will be evaluated using applicable techniques³⁸⁷. In a secondary analysis, additional adjustment for the other potential predictors including baseline biomarkers will be performed.

Chronic Knee Pain. In a separate subcohort of approximately 2000 individuals with baseline chronic daily knee pain and no history of total knee replacement surgery, we will evaluate changes in level of knee pain over the course of the RCT. The annual measure of WOMAC knee pain subscale will be the primary outcome. Angst and colleagues examined data from 122 prospectively-followed individuals with knee OA in a comprehensive rehabilitation program to define the minimally clinically important difference (MCID) in WOMAC scores (range 0-10), for

pain, stiffness and function³⁸⁸. Analgesic use will be secondary outcome, defined on a scale of 0-2: 0 (none), 1 (NSAIDs or acetaminophen only) and 2 (narcotics). As chronic knee pain is associated with age, BMI, medication use, comorbidities and depression (MHI-5), we will again ensure that baseline characteristics are balanced in the four treatment groups in this knee pain subcohort and will additionally adjust for these potential confounders in our analyses. Similarly, we will analyze repeated measures of WOMAC knee pain score, stiffness score, function score and globe score as continuous outcomes. The descriptive statistics and the distribution of each outcome variable will firstly be examined. Transformation will be considered if applicable. We will use two-way analysis of variance (ANOVA) or Kruskal–Wallis test for bivariable analysis and general linear mixed model for multivariable repeated measure analysis. For another secondary outcome, we will assess the effects of the supplements upon analgesic use, classified as: no medications, acetaminophen or non-steroidal use; and narcotic medication). Generalized linear mixed models for repeated binary outcomes will be used to examine the adjusted associations.

Statistical issues in resampling from a RCT. Our investigations of the effects of these agents on biomarkers of systemic inflammation and knee pain will not utilize the entire 20,000 individuals enrolled in the funded VITAL trial. Rather, each will follow a selected subcohort of approximately 2000 individuals. It is possible that these individuals will not be drawn completely equally or randomly from the 4 treatment groups. Possible unbalance of sample characteristics will be evaluated and be controlled for in multivariable analyses.

Secondary Analyses. Beyond the primary analyses, we will examine several pre-specified secondary outcomes for autoimmune diseases, inflammatory biomarkers, and chronic knee pain. We will examine effect modification by the other randomized intervention, by baseline risk factors, and by time. Given past studies showing interactions between intake of n-6 fatty acids and n-3 in reductions in biomarkers of systemic inflammation²⁸⁵, we have a particular interest in exploring interactions between the interventions, as well as with the baseline plasma biomarkers of 25(OH)D for vitamin D and of EPA+DHA for fish oil, and dietary intake of both. We hypothesize that the intervention effects may be larger among those with below-median baseline levels and will examine treatment effects by quartiles of these biomarkers. When stratifying by 25(OH)D, season (assessed by date of return) and geographic location (assessed by zip code) will be considered. We also have a prior interest in the effects of the vitamin D intervention within groups defined by race/ethnicity and skin pigmentation, and by BMI. In addition, we will evaluate effect modification by age and gender, as well as by sunlight exposure, calcium and phosphorus intakes from the FFQ (as these nutrients affect vitamin D bioavailability¹), and baseline risk factors for autoimmune disease, systemic inflammation and chronic knee pain. Interaction effects will be interpreted cautiously, as hypothesis-generating. Finally, we will examine whether treatment effects vary over time and duration of treatment by examining survival plots and interactions with time. There may be latent effects on outcomes, depending on the stage at which these agents act.

Analysis of potential adverse effects. We will also compare the incidence of potential side effects in the active vs. placebo groups for each agent, including the incidence of kidney stones with vitamin D assignment³⁸⁹ and the incidence of GI symptoms, skin abnormalities, and bleeding with fish oil assignment.³²⁹

Power calculations. This section provides a detailed power analysis for each of the 3 aims. To calculate

power, the following assumptions were made: (1) a 2x2 factorial trial in 10,000 men aged ≥ 60 and 10,000 women aged ≥ 65 ; (2) independent and equal allocation of participants to each treatment in the trial (for Aim 1); (3) an age distribution based on that observed at baseline in our past RCTs for men aged ≥ 60 and women aged ≥ 65 ; (4) trial follow-up of 5 years, with little loss to follow-up as achieved in our past RCTs; and (5) compliance of 80% similar to that in published trials upon which our estimated rate ratio (RR) reductions are based. Power calculations were performed using the observed RR, given past observed effects and assuming

a compliance of 80%. The corresponding true relative risk (RR) with perfect compliance is also calculated.

a. Incident autoimmune diseases. As in **table 1**, we estimate the annual incidence of total autoimmune diseases in a U.S. population over age 60 to be approximately 1000 cases per 100,000 individuals per year: thus, in this trial of 20,000 individuals for 5 years, 1000 incident cases. (**Table 2**) Conservatively, we will validate 60% of these 1000 cases, or 600 cases, with 150 occurring in the placebo group and fewer in the intervention groups if they are effective. Given the clustering of autoimmune diseases within individuals, some incident cases will occur within the same individuals, and these will be analyzed as discrete endpoints. Power is given for a a logrank test³⁹⁰ based on the proportional hazard rates with a significance level of 0.05. (**Table 4**) Assuming that only one agent is effective, with 5 years of treatment and follow-up, we will have 81% power to detect an observed RR of 0.70 (or 30% risk reduction) for the primary endpoint of autoimmune disease incidence. For the secondary endpoint of AITD, we will have 85% power to detect a 40% risk reduction. If both agents are effective in preventing autoimmune disease but act independently, power would be reduced slightly due to a somewhat smaller overall number of events. If the agents interact, however, power will be affected to the extent of the interaction. Should the agents act synergistically, power would increase. For example, if the effect of each agent alone is a reduction of 15%, but in combination the effect is stronger, with an additional 10% decrease, the RR comparing the combined group to the all placebo group would be 0.65, versus 0.72 with additive effects (on the multiplicative scale). Power for the total effects would increase to 91%. Power is shown for a given observed reduction in risk, assuming 80% compliance similar to that seen in trials such as WHS and PHS.

Observed RR†	True RR	Autoimmune Disease	AITD
0.70	0.67	0.81	0.62
0.65	0.61	0.91	0.75
0.60	0.56	0.97	0.85

†Observed RR=intent-to-treat RR assuming compliance 80%. True RR= with perfect compliance. AITD= autoimmune thyroid disease

b. Inflammatory biomarkers. Our power calculations are based on past changes in systemic inflammatory biomarkers in large cohort analyses and we have first assumed that only one agent is effective, that compliance is 80% and that the cohort of 2000 followed over two years for changes in biomarkers is randomly drawn from each of the four treatment groups. (**Table 5**) Based on the distribution of hsCRP, IL-6 and TNFR2, natural log-transformation may be used for power analysis if applicable. According to NHANES 1999-2002

Observed reduction %	hsCRP	IL-6	TNFR2
20	0.72	0.55	>0.99
25	0.89	0.74	>0.99
30	0.97	0.88	>0.99
40	0.99	0.99	>0.99

†Assuming compliance to be 80%.

data, median hsCRP level is 2.8 mg/L for men aged ≥60 and women aged ≥65³⁹¹. Using a two-sided type I error of 0.05, the sample size of 500 patients with compliance of 80% in each group will achieve 89% power to detect a 25% reduction of hsCRP using a two-sided t test (based on log-transformed scale). Pai and

colleagues examined plasma levels of TNFR2 and IL-6 as biomarkers for cardiovascular disease risk among participants in the Nurses' Health Study and the Health Professional Follow-up Study (mean age 60.3 for women, 65.2 for men)¹³⁵. The mean TNFR2 was 2370 pg/ml (SD 795 pg/ml) and the median IL-6 level was 1.6 pg/mL. A sample size of 500 per group with compliance of 80% will achieve more than 99% power to detect 20%-40% reduction of TNFR2 with a two-sided significance level of 0.05. Based on a log-transformed scale, we will have 88% power to detect a 30% reduction in IL-6.

c. Chronic knee pain. In the study by Angst and colleagues, the mean global score was 4.8 and the MCID for improvement in pain was 0.75, for stiffness 0.72, for function 0.67 and for global

	Baseline Score	SD	MCID	Power
WOMAC knee pain	4.83	2.25	0.75	0.99
WOMAC knee stiffness	4.61	2.67	0.72	0.96
WOMAC knee function	4.81	2.18	0.67	0.99
WOMAC Global	4.80	2.09	0.67	0.99

SD= standard deviation per Angst, 2002 MCID= minimally clinically important difference

score 0.67³⁸⁸. Assuming a type I error rate of 0.05 and a power of 0.80, this translated into sample sizes of 142, 216, 162, and 153 individuals respectively affording adequate statistical power to detect these changes in an RCT of an intervention using the WOMAC as an outcome. We will follow 2000 individuals with chronic daily knee pain longitudinally over up to 5 years. With estimated loss to follow-up and compliance of 80%, we will have generous statistical power to detect the MCID in improvement in WOMAC pain, stiffness, function and global scores. (**Table 6**) Moreover, repeated measurement of WOMAC scores will provide additional power to detect specified effect sizes. Again, unequal group sample sizes could reduce the power to some extent (although is unlikely to occur unless there is a strong chance imbalance). However, if we conservatively assume the intervention to placebo allocation ratio is 1:2, we will still achieve similar power to detect 25% reduction in both inflammatory biomarkers and the WOMAC MCID of knee pain. (The power to detect MCID for WOMAC knee pain would be > 99%, for WOMAC knee stiffness 95%, and for WOMAC knee function 98%.)

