20,000 men and women, aged ≥ 60 and ≥ 65 , respectively. VITAL cohort assembly has begun and baseline mailings will begin in January 2010. The three outcomes that we will test in this ancillary grant include: prevention of autoimmune diseases, and effects on systemic inflammation and chronic knee pain. At the end of a 3 month run-in period, participants will be randomly assigned to one of four treatment groups for 5 years: vitamin D₃ (2000 IU/d) and fish oil (EPA+DHA, 800 mg/d); vitamin D₃ and fish oil placebo; placebo vitamin D₃ and fish oil; and placebo vitamin D₃ and placebo fish oil. At 1-year intervals, participants will receive a new supply of pills, and assessments of incident autoimmune diseases, compliance and potential side effects. All autoimmune disease endpoints will be confirmed by medical record review by the physician endpoints committee. We anticipate validation of 600 incident cases of autoimmune disease, giving us sufficient statistical power to assess supplement effects on disease incidence. Blood samples at baseline and after 1-2 years follow-up will be collected in a subcohort of 2000 individuals and analyzed for changes in biomarkers of systemic inflammation: C-reactive protein, interleukin-6, and tumor necrosis factor- α . Approximately 2000 individuals with chronic, daily knee pain on baseline screening will be followed with annual questionnaires, providing ample statistical power to evaluate the effects of vitamin D and fish oil upon changes in chronic knee pain. This trial will be very cost-effective as it will be conducted by mail. Each participant will be randomly assigned in a 2x2 factorial design to vitamin D, fish oil, both agents, or both placebos (anticipated mean treatment duration of 5 years).

Study population. The study population will be that of the parent VITAL trial, described in Partners' IRB approved protocol 2009-P-00127; clinicaltrials.gov NUMBER01169259. It will include approximately 20,000 apparently healthy participants—10,000 men aged ≥ 60 and 10,000 women aged ≥ 65 , ages at which rates of chronic diseases, including autoimmune diseases and knee OA pain, increase substantially.

Cohort assembly, eligibility, run-in and randomization are described in Partners' IRB approved protocol 2009-P-00127; clinicaltrials.gov number 01169259.

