aires will be mailed a letter asking them to sign a medical release form authorizing VITAL staff to obtain hospital/physician records. The request will be accompanied by a cover letter expressing sympathy for the diagnosis and explaining guidelines and the scientific importance of record validation. Non-responders will be sent two additional requests for the medical release form. During the 10 year Women's Health Study trial, only 5% of cases refused to sign a medical release. After the release is obtained, a copy will be sent to the treating hospital or physician. If there is no response within 1 month, a second request will be mailed, followed by a phone call. In the Women's Health Study, the staff was able to obtain hospital/physician records 99% of the time.

2. Medical records will be reviewed independently by two trained physicians (including board certified rheumatologist, endocrinologist, and gastroenterologists) blinded to the randomized treatment assignment, will confirm or disconfirm the autoimmune disease according to classification criteria (**Table 3**). The specificity of autoimmune connective tissue disease detection using a staged series design is very high, reducing misclassification of healthy subjects⁴⁰⁶. Similar procedures have been used in the Nurses' Health Study for the validation of RA and SLE by self-report, with case confirmation rates of 69-70% of medical record reviewed^{386, 387}. All participants who report autoimmune diseases that cannot be validated will be censored from analyses at the time of the ambiguous self-report. The primary autoimmune disease endpoint of VITAL will be total autoimmune disease incidence. We estimate that 1000 or more new cases of autoimmune disease should occur during the five years of this trial in this elderly population, although we will not be able to capture them all. We anticipate some over-reporting of incident autoimmune diseases, and may need to mail up to three separate medical record requests in some cases. We estimate a final confirmation of 60% of the true incident cases, or 600 cases. Individuals who report an autoimmune disease at baseline or in follow-up will not be excluded from analyses of other incident autoimmune diseases (e.g., an individual who reported pre-existing AITD will not be excluded from analyses of new autoimmune diseases).

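### Does the rule that censors participants after an unvalidated autoimmune report leave the primary endpoint undefined?

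*Combined protocol and SAP*

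**What the plan says.** The protocol section on incident autoimmune disease ascertainment and validation sets a two-stage procedure: self-report on an annual questionnaire, then blinded review of medical records by two physicians, who "will confirm or disconfirm the autoimmune disease according to classification criteria". Three sentences follow that bear on the risk set:

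- On reports that fail validation: "All participants who report autoimmune diseases that cannot be validated will be censored from analyses at the time of the ambiguous self-report".
- On the endpoint: "The primary autoimmune disease endpoint of VITAL will be total autoimmune disease incidence". The Protocol Biostatistical Analyses section repeats it: "we will estimate the intervention effects on the primary endpoint of total incident autoimmune disease".
- On other diseases: "Individuals who report an autoimmune disease at baseline or in follow-up will not be excluded from analyses of other incident autoimmune diseases". The one example given is a pre-existing thyroid disease.

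The analysis section adds the general principle "Analyses of treatment effects will be based on the intent-to-treat principle" and specifies log-rank and Cox analyses, but gives no further censoring rule. The power section for incident autoimmune disease has a sentence beginning "Given the clustering of autoimmune diseases within individuals", which goes on to say that several diseases in one person will be handled as separate endpoints.

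**The concern.** The censoring sentence is about participants and about analyses in general. Take someone who reports rheumatoid arthritis in year 2, cannot be validated, and has thyroid disease confirmed in year 4. Read literally, the censoring sentence removes the year-4 event. The retention sentence keeps the person at risk for it. Reading the censoring as specific to the reported disease settles the single-disease analyses, but leaves open whether this person's year-4 event counts towards the total.

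There is a second gap. The text does not say whether a report that reviewers actively disconfirm is one that cannot be validated, or whether the term covers only reports that stay unresolved because records were refused or missing.

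The worry is that follow-up for the primary endpoint would end because of something that happens after randomization and may be related to the outcome, since the plan itself expects these diseases to cluster within people. At stake would be confirmed events, some power and, if such reports differed between arms, the rate ratio itself.

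**Working it through.** **1. The plan's own power figure.** The power section expects 600 confirmed cases, 150 of them in the all-placebo cell, and gives 81% power at an observed rate ratio (RR) of 0.70 for a log-rank test at the 0.05 level. The figure reproduces as one cell against another:

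- Events: 150 + 150 × 0.70 = 255.
- z = (√255 / 2) × |ln 0.70| − 1.960 = 7.984 × 0.3567 − 1.960 = 0.888, so power is 81.3%.

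All 600 events would give 99.2%, so the 81% belongs to the 255-event comparison. Proportional losses are applied to that comparison below.

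**2. How many people the rule touches.** The protocol cites 69–70% confirmation of reviewed records in a nurses' cohort, and 5% refusal and 99% record retrieval in an earlier women's trial. That these hold here is an assumption.

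- Records reviewed: 600/0.70 = 857 to 600/0.69 = 870.
- Refused or unobtained: 857/(0.95 × 0.99) − 857 = 54 (55 from 870).
- Not confirmed on review: 857 − 600 = 257 to 870 − 600 = 270.
- Both groups: 311 to 325.

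**3. Events lost if all later follow-up is censored.** The later rate is set to the plan's confirmed rate, 600/(20,000 × 5) = 0.006 a year. The plan assesses disease yearly: "At 1-year intervals, participants will receive a new supply of pills, and assessments of incident autoimmune diseases, compliance and potential side effects". Reports spread evenly over five annual questionnaires leave a mean of (4+3+2+1+0)/5 = 2.0 years; reports spread uniformly over five years leave 2.5. Events lost = people × 0.006 × years; remaining events = 255 × (1 − lost/600).

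| Who is censored | Events lost of 600 | Power at RR 0.70 |
|---|---|---|
| Unobtainable records only (54) | 0.65 (2.0 y) to 0.81 (2.5 y) | 81.2% |
| Also disconfirmed (311 at 2.0 y; 325 at 2.5 y) | 3.7 to 4.9 | 81.0% |

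The largest loss is 4.9/600 = 0.8% of events and about 0.3 power points.

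**4. Effect on the rate ratio.** If the later rate equals the cohort rate, censoring is non-informative by construction. The null RR is then 1.000 under either rule, even if one arm has 20% or 50% fewer such reports. That cannot test the clustering argument, so the later rate was raised, purely as an assumption:

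- At 10 times the cohort rate (0.06 a year) and the largest group, the loss is 325 × 0.06 × 2.5 = 48.8 events and power is 77.9%.
- To move a null RR, the reports must also differ by arm. With 20% fewer in one arm (181 v 144), that arm has (300 − 21.7)/(50,000 − 361) = 0.005607 and the other (300 − 27.1)/(50,000 − 451) = 0.005508. The ratio is 1.018.
- With 50% fewer (217 v 108), it is [(300 − 16.3)/(50,000 − 271)] / [(300 − 32.5)/(50,000 − 542)] = 1.055.

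Both departures must hold together, and the documents support neither figure.

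**5. The sentences side by side.** The retention sentence speaks of other diseases, and the power section treats several diseases in one person as separate endpoints. Both fit censoring that applies to the reported disease. Read that way, the two sentences do not conflict. If the censoring sentence is instead read literally, it covers the total as well, and a rule for the primary endpoint does exist. Each reading yields a workable analysis.

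**The case for a change.** The strongest case for a change is that a plan should fix who is at risk and what counts as a primary event before unblinding. Here two analysts could disagree and each cite the same section. Whether disconfirmed reports are included changes the affected group about sixfold (54 against 311–325). One sentence would settle it, at almost no cost.

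The ambiguity stands: the rule for the total endpoint is not given by name, and the status of disconfirmed reports is left to inference. A clarifying note would do no harm.

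Two stronger claims do not stand. First, intention to treat is not breached. It governs the arm in which a person is analysed; someone censored when disease status becomes indeterminate stays in the assigned arm and contributes time until then. Second, censoring is not plainly the worse rule. It keeps people who may be true but unprovable cases from being counted as disease-free, whereas continued follow-up leaves them in the risk set as non-events. The plan expects to confirm only 60% of 1,000 true cases, so such people may well exist. That is a trade-off. Record review is blinded to treatment, which limits differential misclassification under either rule.

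**Conclusion.** The wording is loose, but the plan needs no change. It leaves out a detail that an analyst can fill sensibly in either of two ways, and the results stay sound under both: less than 1% of primary events, about 0.05 power points under the narrow reading and at most about 0.3 under the broad one, and a null rate ratio of 1.000.

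These sizes assume that confirmation, refusal and retrieval rates from the cited studies carry over, that reports are spread evenly over follow-up, and that unvalidated reporters later develop confirmed disease at the cohort rate. The last matters most. A tenfold rate would cost about 3 power points, and a visible shift in the rate ratio would also need a marked imbalance in such reports between blinded arms. The documents give no figure for either, so those results mark the limits of the conclusion and are not evidence of bias.
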